### *Secondary Performance Endpoints*

The secondary performance endpoint Time to Hemostasis was to evaluate the elapsed time between MANTA deployment and the first observed and confirmed arterial hemostasis. Mean Time to Hemostasis was 2 minutes and 23 seconds (Standard deviation: 6 minutes and 38 seconds; Median: 24 seconds; Minimum: 2 seconds; Maximum: 37 minutes and 10 seconds). For 37 subjects (74%), Time to Hemostasis was reported as  $\leq 1$  minute; for 10 subjects (20%), 1 to 10 minutes were required until hemostasis was achieved; and for 3 subjects (6%), more than 10 minutes and manual pressure were required until hemostasis achievement

The secondary performance endpoint Time to Ambulation was to evaluate the elapsed time between MANTA deployment and when ambulation is achieved. Mean Time to Ambulation was 44 hours and 10 minutes (Standard deviation: 25 hours and 7 minutes; Median: 43 hours and 34

minutes; Minimum: 3 hours and 42 minutes; Maximum: 142 hours and 1 minute). For 5 subjects (10%), Time to Ambulation was reported as less than 24 hours; for 28 subjects (56%) Time to Ambulation was between 24 and 72 hours; and for 6 subjects (12%) more than 72 hours were required until ambulation. Hemostasis was maintained during ambulation for all subjects with available data (n=41).

The secondary performance endpoint Treatment Success was to evaluate the number of subjects that had Hemostasis Success and no Major Complications reported. Treatment Success was achieved in 47 subjects (94%). Absence of Hemostasis Success, as well as presence of one or more Major Complications, occurred in the same 3 subjects.

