### **8.3.3 Final Analysis**

The primary effectiveness endpoint, Time to Hemostasis, will be tested by placing an exact one-sided upper 97.5% confidence bound on the mean Time to Hemostasis. If this upper confidence bound is less than 10 minutes the study will have met its primary effective objective. Time to Hemostasis will not be truncated. In the event that Time to Hemostasis cannot be evaluated because a surgical repair must be performed, Time to Hemostasis for that subject will be imputed using the longest Time to Hemostasis from any subject for whom that datapoint exists. There are no statistical tests of the secondary effectiveness endpoints.

The crude rate of the primary safety endpoint, Major Complications, will be presented as the proportion of subjects with one or more Major Complications, along with its exact one-sided upper 97.5% confidence bound. If a significant number of subjects are lost to follow-up or die due to a reason other than a major complication, the Major Complication rate will also be estimated as a Kaplan-Meier rate. Subjects lost to follow-up will be censored at the date of their last contact. Subjects who die due to a reason other than a Major Complication will be censored at their date of death. An exact one-sided upper 97.5% confidence bound will be placed on the estimated major complication rate at 30 days using the formula given by Peto, Peto, and Armitage. If this upper confidence bound is less than 19.9%, the study will have met its primary safety objective. In addition, the proportion of subjects with each individual Major Complication will be presented along with their two-sided exact 95% confidence intervals.

The secondary safety endpoint, Minor Complications, will be presented as the proportion of subjects with one or more Minor Complications. Minor Complications will be qualitatively assessed against a Clinical Acceptance Criterion of 20%. This CAC will not be statistically tested.

VARC-2 Major Vascular Complications will be reported as another second safety endpoint but will not be statistically tested against a PG or qualitatively assessed against a CAC.

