2.4 Primary Study Hypotheses

2.4.1 Primary Safety Hypothesis

The primary safety hypothesis is that the rate of Major Complications in the Primary Analysis Cohort (the proportion of subjects with one or more Major Complications as defined in Section 2.5.1 below) within 30 days of the procedure is less than the Performance Goal of 19.9%. This Performance Goal was derived from data in the published literature on the use of single or multiple Proglide/Prostar devices in large-bore procedures and from the clinical judgment of expert advisors.

Null hypothesis: The rate of Major Complications within 30 days of the procedure is not less than the Performance Goal of 19.9%.

$$H_0: \pi \geq 0.199$$

Alternative hypothesis: The rate of Major Complications within 30 days of the procedure is less than the Performance Goal of 19.9%.

$H_A: \pi < 0.199$,

where π is the population Major Complication rate. The rate of Major Complications in subjects treated with the MANTA device within 30 days will be presented along with the exact one-sided upper 97.5% confidence bound. If this upper confidence bound is less than 19.9%, the study will have met its primary safety objective.

If more than 13 of the subjects in the Primary Analysis Cohort (5% of the 250 assumed to achieve statistical power) are lost to follow-up or die due to a reason other than a Major Complication, the Major Complication rate will also be estimated from a Kaplan-Meier rate statistical curve. Subjects lost to follow-up will be censored at the date of their last contact. Subjects who die due to a reason other than a Major Complication will be censored at their date of death. An asymptotic one-sided upper 97.5% confidence bound will be placed on the estimated major complication rate at 30 days using the estimated survival curve and the standard error formula given by Peto, Peto, and Armitage¹ in Statistical Note 6. If this upper confidence bound is less than 19.9%, the study will have met its primary safety objective.

In addition, the proportion of subjects with each individual Major Complication will be presented along with their two-sided exact 95% confidence intervals.

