3 DETERMINATION OF SAMPLE SIZE

The sample size for this study was based on the primary effectiveness and safety endpoints of Time to Hemostasis and major complication rate. The population Time to Hemostasis is assumed to be 6 minutes, with a standard deviation of 11 minutes. Based on these assumptions and a normal distribution, 62 subjects will provide 80% power to reject the primary effectiveness hypothesis at a one-sided significance of 0.025.

The population Major Complication rate is assumed to be 13%. Based on this assumption, 250 subjects will provide 80% power to reject the primary safety hypothesis at a one-sided significance of 0.025. Therefore, the necessary sample size is driven by the primary safety endpoint and is 250 subjects.

Assuming a lost to follow-up rate of approximately 5%, the study will treat a total of 263 subjects to ensure an adequate sample size of 250 subjects meeting the 30-day primary safety endpoint.

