4.2 Per Protocol Set

The Per Protocol Set (PPS) is the subset of subjects in the PAC for whom all assessments planned in the protocol were performed with no major protocol deviations. Major protocol deviations will include:

1. Informed Consent procedure violations
2. Inclusion/Exclusion violations
3. Missing/out-of-window by >12 month baseline CTA
4. Missing Time to Hemostasis
5. Missing 30-day visit

Subjects found to have major protocol deviations will be excluded from the PPS. The Per Protocol analysis of the primary and secondary effectiveness endpoints and primary safety endpoints will be used for supportive analysis.

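### The Per Protocol Set excludes subjects for post-treatment data that can be missing because the device failed, so it can drop closure failures and Major Complications already observed

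*SAP*

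**What the plan says.** SAP 4.2 limits the Per Protocol Set to Primary Analysis Cohort subjects "for whom all assessments planned in the protocol were performed with no major protocol deviations". Five major deviations follow. Three concern consent, eligibility and the baseline CTA. The other two are "4. Missing Time to Hemostasis" and "5. Missing 30-day visit". The set is supportive for the primary and secondary effectiveness endpoints and for primary safety.

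Other sections bear on these two items:

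- Protocol 8.3.3 has a rule for a missing time: "In the event that Time to Hemostasis cannot be evaluated because a surgical repair must be performed", the longest time observed in any subject is substituted. SAP 5.1 gives the same surgical example and substitutes the worst value at the same site.
- Protocol 6.5.4 and SAP 6.1.1 list adverse event, device explantation and death among the reasons for discontinuation.
- Protocol 8.1.1 defines the Per-Protocol dataset only by the absence of major protocol violations. It says that results from both datasets will be presented and differences examined. SAP 8 records no change from the planned analyses.
- SAP 2.2.1 puts the primary analysis on the Primary Analysis Cohort. SAP 6.3 puts all safety analyses on the Safety Evaluation Set, which does not fit easily with the Per Protocol safety analysis in SAP 4.2.

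**The concern.** A per-protocol set should be defined by how the study was conducted. The consent, eligibility and CTA items do that. The other two items depend on data collected after the device was used, and the device's own performance can cause those data to be missing.

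- **Missing Time to Hemostasis.** A subject who needed surgical repair, and so has no evaluable time, gets an unfavourable imputed time in the primary analysis. SAP 4.2 does not say whether an imputed time still counts as missing. Read literally it does, and the subject leaves the set. That subject is a Technical Success failure by definition. If the repair was for a device-attributable vascular injury, the subject also has a Major Complication and fails Treatment Success.
- **Missing 30-day visit.** A subject with an adjudicated Major Complication who then dies, or is discontinued before the visit, has a known primary safety outcome but can still be excluded.
- **Completeness condition.** The opening sentence is stricter than the list. Read literally, it drops anyone who missed any assessment, including an ankle/brachial index or the 60-day visit. Two programmers could build two different sets.

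At stake is the comparison that Protocol 8.1.1 promises. In an unblinded single-arm study, agreement between the two sets will be read as robustness. That reading is unsafe if one set loses failures by its definition.

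**Working it through.** **Inputs.** SAP 3: assumed Major Complication rate 13%; 263 treated; Time to Hemostasis mean 6 and SD 11 minutes. SAP 2.4: goals 19.9% and 10 minutes, one-sided upper 97.5% bounds. All removal shares and counts below are assumptions; the documents give none by outcome.

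**The plan's own figures.** The SAP states that "250 subjects will provide 80% power to reject the primary safety hypothesis at a one-sided significance of 0.025". With an exact (Clopper-Pearson) bound, 250 subjects allow at most 37 events; power is 82.7% and one-sided error 2.3%. A one-sample t-test with 62 subjects has 80.5% power for Time to Hemostasis. Both figures hold. With 263 subjects at most 39 events are allowed (14.8%, bound 19.7%), and at a true 19.9% the chance of clearing the goal is 2.1%.

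**Safety: expected rate.** Let p be the true rate, q the share of complication subjects removed and r the share of event-free subjects removed. The rate in the set is p(1−q) / [p(1−q) + (1−p)(1−r)]. With p = 0.13, r = 0 and q = 0.10, 0.20, 0.30 it is 11.9%, 10.7%, 9.5%.

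**Safety: chance of clearing the goal.** Let p = 0.199 and N = 263. Events are binomial, retained events and non-events are binomial given those, and success means a bound below 19.9%.

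| q | r = 0 | r = 0.05 | r = q |
|---|---|---|---|
| 0 | 2.1% | – | 2.1% |
| 0.10 | 8.1% | 4.3% | 2.0% |
| 0.20 | 24.2% | 15.0% | – |
| 0.30 | 51.6% | 38.3% | – |

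**Safety: direction.** Removal lowers the rate only if the removed subjects have a higher event rate than the whole cohort. Take 34/263 = 12.9% (bound 17.6%) and remove 13 subjects:

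- 0 with events: 34/250 = 13.6%, bound 18.5%
- 2 with events: 32/250 = 12.8%, bound 17.6%
- 5 with events: 29/250 = 11.6%, bound 16.2%

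Near the goal the conclusion can change. 40/263 = 15.2% has bound 20.1% and misses. Removing 13 with 3 events gives 37/250 = 14.8%, bound 19.8%, and meets. Removing 13 with none gives 40/250 = 16.0%, bound 21.1%.

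**Time to Hemostasis.** Suppose m subjects have no time because of surgical repair and are imputed at T minutes; the rest have mean 6 and SD 11. The full-cohort mean is M = [6(263−m) + Tm]/263. The variance is [(262−m)·11² + (263−m)(6−M)² + m(T−M)²]/262. The bound is t-based. T = 37.2 is the longest time in the EU study (37 min 10 s); 60 and 90 are assumed.

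| m | T | Full cohort: mean, bound | Per Protocol: mean, bound |
|---|---|---|---|
| 3 | 37.2 | 6.4, 7.7 | 6.0, 7.3 |
| 3 | 90 | 7.0, 8.7 | 6.0, 7.3 |
| 8 | 37.2 | 6.9, 8.4 | 6.0, 7.4 |
| 8 | 90 | 8.6, 10.75 | 6.0, 7.4 |

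For the last row, M = (6×255 + 90×8)/263 = 2250/263 = 8.56, SD 18.06, and bound 8.56 + 1.969×18.06/√263 = 10.75. The cohort misses the 10-minute goal and the Per Protocol Set meets it. The set's mean is lower whenever the imputed time exceeds the mean of the other subjects.

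**The case against.** The strongest reply is that no success decision uses this set. Effectiveness is decided on the Primary Analysis Cohort with worst-value imputation. Safety is decided on the Safety Evaluation Set, with a Kaplan-Meier estimate added if more than 13 subjects are lost or die from another cause. Both effectiveness results are reported, so a divergence would be visible. This stands, and it limits the point to the supportive analysis.

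Three stronger readings are tempting, and the documents do not support them.

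- **That the set always flatters safety.** The items exclude on missing data, not on the outcome itself. Event-free losses, which the crude rate counts as non-events, leave too, and removing them raises the rate.
- **That the 8%, 24% and 52% are type I error for the trial.** A Per Protocol result triggers no claim. These figures also assume that only complication subjects drop. They shrink once event-free subjects drop too, and at equal 10% removal the chance is 2.0%.
- **That the EU study shows such removal.** It reports: "Absence of Hemostasis Success, as well as presence of one or more Major Complications, occurred in the same 3 subjects". But those three had recorded times of 37, 27 and 13 minutes, so the hemostasis item would have removed none of them. The four deaths were judged related to neither device nor procedure.

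It is also fair that the SAP does not state that a death is classed as a missed visit, or that an imputed time counts as missing. Deviations are classified before database lock, so a sensible classification could avoid the problem. That is a reason to write the rule down.

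**Conclusion.** The point holds for the supportive analyses only. As written, SAP 4.2 can remove surgical-repair subjects and subjects whose Major Complication is already known.

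- **Effectiveness.** If the time is missing because of surgical repair and the literal reading applies, the bias favours the device. The full-cohort mean exceeds the Per Protocol mean by about 0.4 minutes with 3 such subjects imputed at 37.2 minutes, and by 2.6 minutes with 8 at an assumed 90.
- **Safety.** Bias is possible and its sign is not fixed. The illustration at a true 19.9% runs from no inflation (equal removal) to 52% (30% of complication subjects and nobody else), and rests wholly on assumed shares.
- **Definition.** The completeness condition and the five-item list describe different sets. No direction of bias is shown for the stricter one.

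The primary conclusions and the sample sizes are unaffected. The change should be made because it is cheap and makes the promised comparison between the two sets informative.

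**What to change.** Amend SAP 4.2 as follows.

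- **(a)** Limit the hemostasis item to times missing for administrative reasons. Keep surgical-repair and failed-closure subjects in the set with the imputed time.
- **(b)** Do not exclude for a missed 30-day visit as such. Keep every subject with an adjudicated Major Complication as an event, and handle death or loss without one by the censoring already described in SAP 2.4.1. If event-free subjects who missed the visit are still excluded, state that this selects on outcome, raises the rate (34/263 = 12.9% becomes 34/250 = 13.6% with 13 removed) and is conservative.
- **(c)** Delete the completeness condition from the opening sentence, so that the listed deviations alone define the set.

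The cost is SAP wording only, with no extra subjects or data. The consent, eligibility and CTA exclusions stay. The downside is that the Per Protocol results may look slightly less favourable.

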4.3 Safety Evaluation Set

The Safety Evaluation Set (SES) will consist of all non-roll-in subjects in whom an attempt to use the MANTA device was made. (i.e., subjects who sign the consent form but are deemed ineligible for the study prior to any attempt to use the MANTA device will not be included in the safety analyses). Subjects who are excluded due to intra-procedural exclusions will be excluded from the safety analyses as long as the MANTA sheath has not been introduced; use of the MANTA puncture locator at the beginning of the procedure is not considered "attempted use" of the MANTA device. The Safety population will be used for the analysis of safety endpoints as well as procedural and discharge data.

4.4 Roll-In Cohort

Up to two roll-in subjects per operator using either MANTA device will be enrolled to allow investigators to learn how to use the MANTA device. Data from the Roll-In Cohort will be summarized separately from the Primary Analysis Cohort for safety and effectiveness and will not be tested statistically against the Performance Goals.

5 DATA CONVENTIONS AND DEFINITIONS

5.1 Handling of Missing Data

Missing data will not be imputed for safety endpoints. However, if more than 13 subjects in the Primary Analysis Cohort either die for a reason other than a Major Complication or are lost to follow up within 30 days of treatment, then the rate of Major Complications will also be estimated by the Kaplan-Meier method, to allow for subjects who are censored before a Major Complication can be observed. See Section 2.4.1 for further details.

For effectiveness endpoints, it is highly unlikely that there will be missing data for Time to Hemostasis, Technical Success, Ambulation Success, Time to Ambulation, Treatment Success or Procedure Time. However, if any of these data are missing (i.e., in the event that Time to Hemostasis cannot be evaluated because a surgical repair must be performed), the worst value observed for any subject at the same study site within each analysis cohort, will be imputed for the missing value. Missing data for a subject in the Primary Analysis Cohort will be imputed with the worst value observed for any Primary Analysis Cohort subject at the same study site, and missing data for a subject in the Roll-In Cohort will be imputed with the worst value observed for any roll-in subject at the same study site.

No other imputations will be carried out for missing data.

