## **6 Study Design**

### **6.1. General**

A prospective, multi-center, single-arm clinical investigation to evaluate the safety and effectiveness of MANTA in achieving hemostasis in femoral arterial access sites in patients undergoing percutaneous transcatheter interventional procedures using large-bore sheaths or devices. The study will evaluate Time to Hemostasis, Technical Success, Treatment Success, Ambulation Success, Time to Ambulation, Procedure Time, and the rate of access-site-related Major and Minor Complications in comparison to Performance Goals and a Clinical Acceptance Criterion derived from published literature on other hemostasis techniques for closing these large bore punctures (suture-mediated percutaneous closure [i.e. multiple Proglide/Prostar devices]) (see Appendix 2) and based on the clinical judgment of expert advisors. The study will be conducted at a minimum of 5 and up to 25 investigational sites in the U.S., EU and/or Canada.

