### **8.3.6 Missing Data**

It is highly unlikely that there will be missing data for Time to Hemostasis, Technical Success, Ambulation Success, Time to Ambulation, Treatment Success or Procedure Time. However, if any of these endpoints are missing, the worst value observed for any subject at the same study site will be imputed for the missing value.

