## **8.4. *Minimum and Maximum Subject Recruitment for Analysis***

Study enrollment will be competitive. There is no minimum number of subjects that can be enrolled per site. However, no single site will be permitted to enroll more than 20% of the Analysis Cohort enrollment (i.e., 50 treated subjects).

There is also no minimum or maximum number of subjects defined in order to be included in the statistical analysis.

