5.2 Poolability Analysis and Stratification

Analyses of the primary effectiveness and primary safety endpoints will be performed to assess the comparability of study sites. Sites with fewer than 5 subjects each will be pooled into a composite site.

Time to Hemostasis in the Primary Analysis Cohort population will be analyzed by a one-way analysis of variance that includes the effect of the study site. If the study site means differ ($p<0.15$) then additional analyses will be performed to explore the cause of the difference, in particular if the differences are caused by differences in some baseline factor.

Major Complications in the Safety population will be analyzed by Pearson's chi square to assess if the Major Complication rates differ among study sites. If the study site rates differ ($p<0.15$) then additional analyses will be performed to explore the cause of the difference, in particular if the differences are caused by differences in some baseline factor.

Stratified analyses will not be performed.

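### When surgical repair makes Time to Hemostasis unevaluable, Protocol 8.3.3 imputes the longest time in the study, but SAP 5.1 imputes the same-site worst value without declaring a change, and no fallback covers a site with no donor

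*SAP*

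**What the plan says.** **Protocol 8.3.3** deals with one event on its own. A TTH that cannot be evaluated because of surgical repair is "imputed using the longest Time to Hemostasis from any subject for whom that datapoint exists". The same section says that TTH is not truncated, so long times count in full.

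**Protocol 8.3.6** is the general rule for missing effectiveness endpoints and lists TTH among them: "the worst value observed for any subject at the same study site will be imputed for the missing value". It does not mention surgical repair or say how it relates to 8.3.3.

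**SAP 5.1** takes as its case of missing data a TTH that is unavailable "because a surgical repair must be performed), the worst value observed for any subject at the same study site within each analysis cohort" being the value imputed. It restricts donors to the subject's own cohort and ends: "No other imputations will be carried out for missing data".

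**SAP 8**, the place for changes to the planned analyses, records none, although SAP 1 says the plan is based on Protocol Rev. F.

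Two further provisions matter. On site size, Protocol 8.4 says "There is no minimum number of subjects that can be enrolled per site". On the dataset, Protocol 8.1.1 restricts the primary effectiveness dataset to subjects who have a TTH assessment, while SAP 4.1 keeps every non-roll-in subject in whom the device was attempted.

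**The concern.** One event has two prescribed values, and the SAP's closing sentence prevents the protocol's value from being used. The event is a closure that ended in surgery, and the direction is one-sided: the worst time at one site is at most the worst time in the study. In a small site it could be very short. In the EU study 74% of subjects had hemostasis within 1 minute.

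The rule is also incomplete. If the repaired subject is the only cohort subject at the site, or no other TTH was observed there, neither Protocol 8.3.6 nor SAP 5.1 supplies a value. A literal reading of Protocol 8.1.1 could even drop the subject before imputation.

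The trial is unblinded and single-arm, and it is judged on whether the upper bound for an untruncated mean lies below 10 minutes. If the conflict is found after database lock, the sponsor will be asked which rule was chosen, and when.

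**Working it through.** **Plan's own figure.** Mean 6, SD 11, goal 10, one-sided 0.025. The normal formula, (11 × (1.960 + 0.842)/4)², gives 60. With the one-sample t test, power is 0.798 at N = 61 and 0.805 at N = 62. The stated 62 is reproduced and is not in dispute.

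**Direction.** Each SAP-imputed value is at most the protocol-imputed value, so the mean is too. The bound, mean + t × SD/√N, also rises with any single value unless that value lies more than about 8.2 SDs below the mean (√263/1.969 × 262/263). That cannot happen for a non-negative time with these means and SDs. The SAP bound is therefore never above the protocol bound.

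**Inputs.**
- N = 263 (Protocol 6.5.1).
- EU study (Protocol 1.4): mean 2 min 23 s = 2.38; SD 6 min 38 s = 6.63; 74% at or below 1 min, 20% at 1-10 min, 6% above; the three long times were 13, 27 and 37 min, with a maximum of 37 min 10 s = 37.17.
- Sites: the protocol plans "at a minimum of 5 and up to 25 investigational sites", and "no single site will be permitted to enroll more than 20% of the Analysis Cohort enrollment", stated as 50 treated subjects. 263/50 = 5.26, so at least 6 sites are needed.
- Number imputed, r: not in the documents, so assumed. All 50 EU subjects had a TTH. 0/50 has an exact two-sided 95% upper limit of 1 − 0.025^(1/50) = 7.1%, or 18 of 263. I take that as the top of the range.

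**Expected same-site worst value, EU-like.** Assume equal sites and 2% of subjects at each of 13, 27 and 37.17 min. With n donors, the site maximum is 37.17 with probability 1 − 0.98ⁿ, 27 with 0.98ⁿ − 0.96ⁿ, 13 with 0.96ⁿ − 0.94ⁿ, and otherwise at or below 10 min (about 9 with many donors, about 6 with few, if times are uniform within bands).
- 6 sites, n ≈ 43: 37.17 × 0.58 + 27 × 0.25 + 13 × 0.10 + 9 × 0.07 ≈ 30 min.
- 25 sites, n ≈ 9.5: 37.17 × 0.175 + 27 × 0.147 + 13 × 0.123 + 6 × 0.556 ≈ 15.5 min.

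**Bounds.** Combine 263 − r observed subjects (mean 2.38, SD 6.63) with r imputed values; t(0.975, 262) = 1.969.

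| r = 5, EU-like | Imputed value | Mean | Upper bound |
|---|---|---|---|
| Protocol 8.3.3 | 37.17 | 3.05 | 4.03 |
| SAP 5.1, 6 sites | 30 | 2.91 | 3.83 |
| SAP 5.1, 25 sites | 15.5 | 2.63 | 3.46 |

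The bound differs by 0.20 min with 6 sites and 0.57 with 25. Simulating whole trials, with both imputed values drawn from the same trial, gives about 0.2 and 0.55-0.6.

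**Distance from 10 minutes.** With r = 18 at 37.17 min the EU-like bound is 6.09. It takes 45 such values to reach 10, or 20 if the other subjects follow the planning mean and SD. In EU-like simulations (6, 8, 13 and 25 sites; r = 1, 5, 8 and 18) the two rules never disagreed on pass or fail.

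**Less favourable case.** Suppose TTH has mean 6 and SD 11 and is skewed: gamma with shape (6/11)² = 0.298 and scale 121/6 = 20.2, or lognormal. The median longest time is then 75-85 min. Over 6 to 25 sites the rules disagree in roughly 0.5-4% of trials with one imputed value and 5-17% with three; the lognormal gives the upper ends. Every disagreement is a SAP pass and a protocol fail.

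**Small sites.** With independent donors at the EU share of 74%, the chance that every donor is at or below 1 min is 74% with 1 donor, 0.74³ = 41% with 3 and 0.74⁵ = 22% with 5. One failed closure imputed at 1 rather than 37.17 min moves the mean by 36.17/263 = 0.14 min.

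**The case against.** The SAP did not invent its rule. Protocol 8.3.6 already prescribes the same-site worst value and names TTH, so the tension begins inside the protocol. The missing fallback is in 8.3.6 as well. This stands, and it tempers the point about SAP 8. It does not remove the conflict: 8.3.3 is specific to surgical repair and would have no function if the general rule covered that event.

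Unevaluable TTH should be rare. Both documents call missing effectiveness data highly unlikely, compression time counts towards TTH, surgery comes last in the management sequence (Protocol 7.6), and SAP 6.2.3 lists surgical repair as a way in which hemostasis is obtained. This also stands and is the main reason the expected effect is small.

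A reader might infer that failed closures would be hidden. The documents do not support that. Device-attributable vascular injury needing surgical repair is a Major Complication and so also fails Treatment Success. Unplanned surgery fails Technical Success. Surgical repair is tabulated among the adjunctive methods.

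A reader might also take "Sites with fewer than 5 subjects each will be pooled into a composite site" to mean that the SAP expects small sites, or that the composite could supply donors. It is a contingency for assessing site comparability and says nothing about imputation. The no-donor case rests only on the absence of a site minimum.

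**Conclusion.** The conflict holds. For TTH not evaluable because of surgical repair, the protocol and the SAP prescribe different values. The SAP value is equal to or more favourable to the device, the change is undeclared, and the same-site rule has no fallback in either document.

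Its size is modest: about 0.2 to 0.6 min on the upper bound for five imputed values with EU-like times and equal sites, with no change in the result. A reader might infer that the choice of rule decides the primary effectiveness conclusion. That would need several unevaluable repairs together with times much longer than the EU study showed (mean 6 rather than 2.4 min, longest about twice the observed 37 min) and an assumed gamma or lognormal shape. The documents give no probability for that combination. Nor do they show that the SAP rule was chosen for its direction.

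This should be fixed because it concerns the primary endpoint and there should be one complete rule before the data are seen. It is not a threat to the trial's validity.

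**What to change.** Edit the SAP only; the protocol's rule can stand.

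- **SAP 5.1:** remove surgical repair as the example under the same-site rule. State that TTH not evaluable because of surgical repair is imputed with the longest TTH observed at any site, per Protocol 8.3.3.
- **Donors:** say whether roll-in subjects can be donors. Protocol 8.3.3 has no cohort limit, so restricting donors to the Primary Analysis Cohort narrows it and must be declared.
- **Fallback:** if TTH is missing for another reason and the site has no observed TTH, use the same study-wide value.
- **Dataset:** state that subjects with unevaluable TTH stay in the Primary Analysis Cohort as SAP 4.1 defines it, despite the wording of Protocol 8.1.1. The Per Protocol Set excludes missing TTH (SAP 4.2) and is unaffected.
- **SAP 8:** list any departure from the protocol that remains.
- **Reporting:** give the number of imputed TTH values.

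The cost is a few sentences and no new data. Clarifying Protocol 8.3.6 as well would need the full amendment approvals (Protocol 14.1 and 15) and is not necessary. The downside is that the reported mean TTH and its upper bound may be slightly less favourable.
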